3.4 CONCENTRATION-TIME PROFILES

Individual (for each subject) and mean plasma VIR-2218 and metabolite (A-312327) concentrations will be displayed graphically in linear and semi-logarithmic plots versus time (hour) Part, Dose Level, and Dosing Day 1 and Day 29. The actual collection time will be used for plots of individual plasma concentrations and nominal time will be used for plots of mean plasma concentrations. Below the plots, the number of quantifiable concentrations per timepoint will be displayed. Subjects with dosing deviations will be excluded from the mean plots. They will be displayed in the individual plots with footnote.

3.5 Estimation of Pharmacokinetic Parameters

Pharmacokinetic (PK) parameters will be estimated using Phoenix WinNonlin® software using standard noncompartmental methods. The linear/log trapezoidal rule will be used in conjunction with the appropriate noncompartmental model, with input values for dose level, dosing time, PK concentration, and corresponding real time values, based on drug dosing times whenever possible.

All predose sample times before time-zero will be converted to zero.

For area under the curve (AUC), samples below the limit of quantitation (BLQ) of the bioanalytical assays occurring prior to the achievement of the first quantifiable concentration will be assigned a concentration value of zero to prevent overestimation of the initial AUC. Samples that are BLQ at all other time points will be treated as missing data in WinNonlin. The nominal time point for a key event (e.g., plasma collection) or dosing interval (τ) may be used to permit direct calculation of AUC over specific time intervals.

Pharmacokinetic parameters such as AUC_{inf} , λ_z , and $t_{1/2}$ are dependent on an accurate estimation of the terminal elimination phase of drug. The appropriateness of calculating these parameters will be evaluated upon inspection of PK data on a profile-by-profile basis by the PK scientist.

The following parameters will be used to evaluate the PK objectives of the study: T_{max} , C_{max} , T_{last} , C_{last} , $t_{1/2}$, AUC_{0-t} , AUC_{0-8hr} , AUC_{0-12hr} , AUC_{0-24hr} , AUC_{inf} , λ_z , CL/F , V_z/F .

- T_{max} : The time to attain C_{max} . If the same C_{max} concentration occurs at different time points, t_{max} is assigned to the first occurrence of C_{max} .
- C_{max} : Individual maximum concentration (C_{max}) values are directly determined from the plasma concentration time profiles for each subject.
- T_{last} : Time of last measurable (positive) observed concentration.
- C_{last} : Observed concentration corresponding to T_{last} .
- $t_{1/2}$: The terminal half-life will be calculated from the terminal rate constant using the equation:

$$t_{1/2} = \frac{\ln(2)}{\lambda_z}$$

- AUC_{0-t} : The areas under the curve spanning time interval from 0 to t (up to the last time point with measurable concentration). AUC_{0-t} will be calculated using the linear-up /logarithmic-down trapezoidal rule. Linear trapezoidal rule: The area of the trapezoid between the two data points (t_1, C_1) and (t_2, C_2) where $C_2 \geq C_1$ will be computed by:

$$AUC_{t_1-t_2} = 0.5(t_2 - t_1)(C_1 + C_2)$$

Logarithmic trapezoidal rule: The area of the trapezoid between the two data points (t_1, C_1) and (t_2, C_2) where $C_2 < C_1$ will be computed by

$$AUC_{t_1-t_2} = \frac{((t_2 - t_1)(C_1 - C_2))}{\ln C_1 - \ln C_2}$$

- When a partial AUC(e.g. AUC_{0-12hr}) is requested at time points not included in the scheduled measurements scheme, Interpolation will be used to estimate the concentration of these time points.
 - Additional point before last observed data point
Depending on the choice of the “Integral method” setting, this can be done using a linear or log formula to find the added concentration C* at requested time t*, given that the previous and following measurements are C1 at t1 and C2 at t2.
Linear interpolation formula:

$$C^* = C_1 + \left| \frac{t^* - t_1}{t_2 - t_1} \right| \times (C_2 - C_1)$$

Logarithmic interpolation formula:

$$C^* = \exp \left(\ln(C_1) + \left| \frac{t^* - t_1}{t_2 - t_1} \right| \times (\ln(C_2) - \ln(C_1)) \right)$$

If the logarithmic interpolation rule fails in an interval because C1 or C2 are null or negative, then the linear interpolation rule will apply for that interval.

- Additional point after last observed data point
If λ_z is not estimable, the partial area will not be calculated. Otherwise, λ_z is used to calculate the additional Concentration C*

$$C^* = \exp(\text{Lambda_z_intercept} - \lambda_z \times t_{\text{last}})$$

Where Lambda_z_intercept is the intercept on log scale estimated via linear regression of time vs. log concentration in estimating λ_z

- AUC_{0-8hr}: The area under the plasma concentration-time curve over the time interval from 0 to 8 hr using the linear-up /logarithmic-down trapezoidal rule.
- AUC_{0-12hr}: The area under the plasma concentration-time curve over the time interval from 0 to 12 hr using the linear-up /logarithmic-down trapezoidal rule.
- AUC_{0-24hr}: The area under the plasma concentration-time curve over the time interval from 0 to 24 hr using the linear-up /logarithmic-down trapezoidal rule.
- AUC_{inf}: The area under the plasma concentration-time curve over the time interval from 0 extrapolated to infinity will be calculated according to the following equation:

$$AUC_{0-\infty} = AUC_{0-t} + \frac{C'_t}{\lambda_z}$$

where C't is the predicted concentration at the time t (last time point with a measurable plasma concentration above the quantification limit) at which quantification was still possible, the calculation of λ_z is given below.

- AUC_{%extrap}: The percentage of the AUC that has been extrapolated beyond the last observed data point, calculated as:

$$AUC_{\%extrap} = \left(\frac{AUC_{0-\infty} - AUC_{0-t}}{AUC_{0-\infty}} \right) * 100$$

- λ_z : The apparent terminal rate constant λ_z will be estimated from a regression of $\ln(C)$ versus time over the terminal log-linear drug disposition portion of the concentration-time profiles. To calculate the elimination rate constant, the terminal data from a concentration-time curve will be used. Starting with the final non-BLQ data point and moving backwards, toward time zero, at least 3 data points not included C_{max} are fit to a linear regression. The number of data points used can be determined by maximizing the value adjusted- r^2 which defines the “best-fit” of the data. The first order rate constant associated with the terminal (log-linear) portion of the curve will be estimated via linear regression of time vs. log concentration. The rules are that a minimum of three points is needed to define the terminal (log-linear) portion of the curve, λ_z must be positive, and the selection is based on the best adjusted square coefficient of regression (r^2). Additionally, if the adjusted r^2 does not improve, but is within 0.0001 of the largest adjusted R^2 value, the regression with the larger number of points is used. The “adjusted” r^2 is calculated using the following equation:

$$Adjusted\ r^2 = 1 - (1 - r^2) * \frac{(n - 1)}{(n - 2)}$$

where n = the number of data points used in the regression. The slope of the line is equal to $-\lambda_z$ (i.e., the slope will be negative, but λ_z is a positive value).

If terminal concentration-time point(s) increases, this time point may be included if the $t_{1/2}$ estimate is reasonable. If λ_z is not determinable (for example, adjusted- r^2 value <0.8) then consequently only parameters not requiring λ_z will be reported. In addition, the lower (R_{start}) and upper (R_{end}) limit on time (h) for values to be included in the calculation of λ_z will be listed.

- CL/F: The total clearance will be calculated as following:

$$CL/F = \frac{D}{AUC_{0-\infty}}$$

where D is dose

V_z/F : The apparent volume of distribution based on terminal phase will be calculated according to the follow equation:

$$V_z/F = \frac{CL/F}{\lambda_z}$$

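### PK SAP 3.5 prints t_last where the requested time t* is meant in the formula for a concentration after the last observed point (one-symbol correction, minor)

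*SAP*

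**What the plan says.** PK SAP 3.5 sets a rule for the case where a partial AUC "is requested at time points not included in the scheduled measurements scheme", with AUC0-12 as its example. For a point before the last observation, a linear or logarithmic formula is used "to find the added concentration C* at requested time t"* (the asterisk belongs to the symbol t*), and both formulas contain t*.

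For a point after the last observation, if λz "is not estimable, the partial area will not be calculated". Otherwise the concentration is "C^* = \exp(\text{Lambda_z_intercept} - \lambda_z \times t_{\text{last", which reads C* = exp(Lambda_z_intercept − λz × t_last). The same section defines T_last as the time of the last measurable concentration, and the intercept as that of the regression of log concentration on time.

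The AUCinf formula in 3.5 uses a separate symbol, C't, which "is the predicted concentration at the time t (last time point with a measurable plasma concentration above the quantification limit").

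Four other provisions matter:

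- **Sampling (2.2, Table 1).** Post-dose samples are at 1, 2, 4, 8 (± 30 minutes) and 24 h (± 2 hours). There is no 12 h sample.
- **λz (3.5).** "at least 3 data points not included C_{max} are fit to a linear regression". If λz cannot be determined, for example with adjusted r² below 0.8, "then consequently only parameters not requiring" λz are reported.
- **Extrapolated areas (3.6).** When t_last falls short of 24 h (or 8 h), AUC0-24 (or AUC0-8) is reported only if AUC%extrap is below 20%, and such values enter the summary statistics.
- **Metabolite ratio (3.3.3).** It uses AUC0-8, AUC0-12, AUCinf and Cmax, but not AUC0-24.

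**The concern.** A rule for a concentration later than t_last cannot have t_last as its only time argument. Read as written, it gives the same number whether 12 h or 24 h is requested, and that number is the quantity already called C't. No other section of the SAP corrects it.

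Because the fitted curve declines (λz must be positive), the printed C* is always larger than the fitted value at t*. Both trapezoidal rules increase with the end concentration, so the partial area is overstated. At stake are the descriptive summaries of partial AUCs and, through AUC0-12, the metabolite-to-parent ratio. The SAP is also the text against which a programmer or quality-control check would verify the software output: as printed, a correct value would fail that check.

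**Working it through.** **Algebra (no assumption about the profile).** The fitted line gives C(t) = exp(intercept − λz·t). Dividing the printed C* by the fitted value at t* gives exp(λz·(t* − t_last)), which exceeds 1 whenever t* > t_last.

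**Inputs for the size.** From the PK SAP: linear-up/log-down rule, sampling times, late BLQ samples treated as missing, and the three-point rule for λz. Assumed, because the documents say only that the half-life is short: half-lives of 1, 2, 2.5 and 3 h; Tmax 1 h; C(1 h) = 100; exact log-linear decline; 24 h sample BLQ, so t_last = 8 h. The 2, 4 and 8 h points then satisfy the three-point rule.

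**Worked case, half-life 3 h** (C = 100, 79.37, 50.0, 19.84 at 1, 2, 4, 8 h).

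- λz = ln 2 / 3 = 0.23105. AUC0-8 = 0.5 × 100 + (100 − 19.84)/0.23105 = 396.93.
- Tail = 19.84/0.23105 = 85.88, so AUCinf = 482.81 and AUC%extrap = 17.8%.
- Printed C* = 19.84 at both 12 h and 24 h. With t*: 7.87 at 12 h and 0.49 at 24 h.
- AUC0-12 with t*: 396.93 + (19.84 − 7.87)/0.23105 = 448.73. As printed: 396.93 + 4 × 19.84 = 476.30, or +6.1%.
- AUC0-24 with t*: 396.93 + (19.84 − 0.49)/0.23105 = 480.68. As printed: 396.93 + 16 × 19.84 = 714.41, or +48.6% and 148% of AUCinf.

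**All four half-lives, t_last = 8 h.**

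| Half-life | C(8 h) | AUC0-8 | AUCinf (tail) | AUC0-12, t* / printed | AUC0-24, t* / printed |
|---|---|---|---|---|---|
| 1 h | 0.781 | 193.14 | 194.27 (0.6%) | 194.20 / 196.27 (+1.1%) | 194.27 / 205.64 (+5.9%) |
| 2 h | 8.839 | 313.04 | 338.54 (7.5%) | 332.16 / 348.39 (+4.9%) | 338.44 / 454.46 (+34%) |
| 2.5 h | 14.359 | 358.89 | 410.67 (12.6%) | 393.59 / 416.32 (+5.8%) | 410.06 / 588.63 (+44%) |
| 3 h | 19.843 | 396.93 | 482.81 (17.8%) | 448.73 / 476.30 (+6.1%) | 480.68 / 714.41 (+49%) |

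In every row the printed AUC0-24 exceeds AUCinf, which is impossible for a partial area.

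**Sampling window.** Actual times are used where possible, so t_last can be 7.5 h. AUC0-12 then becomes:

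- Half-life 2 h: 308.21 + 4.5 × 10.511 = 355.51 against 332.16 (+7.0%).
- Half-life 3 h: 386.41 + 4.5 × 22.272 = 486.64 against 448.73 (+8.4%).
- Half-life 3.2 h: 398.72 + 4.5 × 24.464 = 508.81 against 469.05 (+8.5%), about the maximum for this profile.

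The AUC0-24 excess also grows: at 3 h, 386.41 + 16.5 × 22.272 = 753.90 against 480.68 (+57%, tail just under 20%).

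**Small cases.** AUC0-8 with the 8 h sample at 7.5 h, half-life 3 h: 386.41 + 0.5 × 22.272 = 397.55 against 396.93 (+0.16%). AUC0-24 with a quantifiable sample at 22 h: about 0.2% or less for half-lives of 2 to 6 h.

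**Metabolite ratio on AUC0-12 (t_last 8 h).** Multiplied by 1.011 to 1.061 if only the metabolite is affected, by 0.989 to 0.942 (the reciprocals) if only the parent is, and by less if both are.

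**The 20% rule.** AUC%extrap is built from C't/λz and does not contain C*. All four rows pass it. For this profile it suppresses AUC0-24 only above a half-life of about 3.2 h.

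**The case against.** The strongest reply is that nothing shows the printed line will ever be executed. PK "parameters will be estimated using Phoenix WinNonlin® software using standard noncompartmental methods", and 3.5 refers to a setting for the integration method, so the text may only describe what the software does. If WinNonlin applies t* internally, results are right and only the text is wrong. This stands: the documents establish a text error, not an error in any result.

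Second, the large percentages lie outside the rule's literal scope. It is written for unscheduled times, and 24 h is scheduled. This also stands in part. AUC0-12 is the parameter clearly covered. Applying the line to AUC0-24 is an inference from 3.6, which extrapolates AUC0-24 when t_last is below 24 h, and from the absence of any other formula for a concentration after t_last.

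Third, a material effect arises only in narrow circumstances. With Tmax at 2 h and t_last at 8 h, or with t_last at 4 h, fewer than three points follow Cmax and the partial area is withheld. A quantifiable 24 h sample means that AUC0-12 is interpolated and unaffected. An AUC0-24 above AUCinf would also be visible in the individual listings.

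Fourth, the test profile lies exactly on the fitted line, so the printed formula holds the curve flat after t_last. With real scatter the observed last value differs from the fitted one and the segment slopes. The percentages would change, but not the direction of the error.

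A reader might infer that reported exposures will be inflated by up to half, or that AUC0-12 cannot be wrong by more than about 6%. The documents support neither. The first needs literal execution, the inferred reach to AUC0-24 and an assumed half-life. The second holds only at the nominal 8 h time.

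**Conclusion.** The formula is wrong as written, and this follows from the SAP's own definitions without any assumption. The size is conditional on literal execution and on the assumed profile. AUC0-12 is the firm case, and its percentages are modest. The larger AUC0-24 figures rest additionally on an inferred reach of the rule, and the 20% safeguard would not detect them. How often the situation would arise is unknown, because no half-life, Tmax or LLOQ value is given.

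PK is a secondary, descriptive objective. Cmax, AUC0-t, AUCinf, CL/F, half-life and the primary safety endpoints do not use this line. Severity: minor.

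**What to change.** In PK SAP 3.5 replace t_last with t*, so that C* = exp(Lambda_z_intercept − λz × t*). Then run one test profile through WinNonlin with the planned settings: predose 0 and C = 100, 79.37, 50.0, 19.84 at 1, 2, 4, 8 h, with 24 h BLQ. Confirm AUC0-12 = 448.7 and AUC0-24 = 480.7. The cost is one symbol and one software check.

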3.6 Other important PK considerations

- The value of $AUC_{\%extrap}$ will be less than or equal to 20% for the $AUC_{0-\infty}$ to be considered well estimated. If this proportion is $> 20\%$, then the values of $AUC_{0-\infty}$ will be treated with caution, and emphasis will be placed on AUC_{0-t} values (i.e. in subsequent statistical analyses).
- If $AUC_{\%extrap} > 20\%$, all elimination related parameters (λ_z , $AUC_{0-\infty}$, $t_{1/2}$, CL/F or CL/F,ss, and V_z/F or $V_z/F_{,ss}$) will be presented in the listings but excluded from the calculation of summary statistics. All values excluded from the summaries should be flagged in the individual listings with an explanation for the exclusion.
- If data permits, the other PK parameters may be reported.
- If $t_{last} = t_{max}$; C_{max} will not be reported for that subject in the listings. It will be footnoted to indicate that sampling timepoints were not appropriate for that subject.

- If $t_{last} < 24\text{hr}$, $AUC_{0-24\text{hr}}$ will only be reported when $AUC\%_{\text{extrap}} < 20\%$; it will be presented in the listing with footnote to indicate that $AUC_{0-24\text{hr}}$ was extrapolated. In the summary tables, the cohort will be footnoted to indicate that subjects with extrapolated $AUC_{0-24\text{hr}}$ were included in the calculation of summary statistics.
- If $t_{last} < 8\text{hr}$, $AUC_{0-8\text{hr}}$ will only be reported when $AUC\%_{\text{extrap}} < 20\%$; it will be presented in the listing with footnote to indicate that $AUC_{0-8\text{hr}}$ was extrapolated. In the summary tables the cohort will be footnoted to indicate that subjects with extrapolated $AUC_{0-8\text{hr}}$ were included in the calculation of summary statistics.

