Calculated PK parameters will be listed and summarized descriptively, including n, arithmetic mean, SD, minimum, median, maximum, coefficient of variation [CV(%)], geometric mean, geometric SD, geometric CV%; For time-related PK parameters (ie., T_{max} , T_{last} and $t_{1/2}$) only n, minimum, median, and maximum will be reported. When reporting individual values and descriptive statistics for PK parameters of VIR-2218 and its metabolite (A-312327), the following rules will apply to rounding and precision:

- Individual values for PK parameters will be reported to 3 significant figures.
- Descriptive statistics for PK parameters will be reported to 3 significant figures.
- Between-subject CV% and geometric CV% will be reported as a percentage to 1 decimal place.
- Data listings containing all documented data and all derived data will be generated. Missing data will not be imputed.
- Subjects with dosing deviations will be reported in the listings but excluded from the summary tables.

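### PK SAP 3.6 withholds Cmax whenever t_last equals t_max, even if the next scheduled sample was drawn and found BLQ, and does not say how the summaries or the Cmax ratio treat it

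*SAP*

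**What the plan says.** PK SAP 3.6 has one unconditional rule: if t_last equals t_max, the subject's Cmax value "will not be reported for that subject in the listings. It will be footnoted to indicate that sampling timepoints were not appropriate for that subject".

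PK SAP 3.5 defines T_last as "Time of last measurable (positive) observed concentration" and C_last as the "Observed concentration corresponding to" T_last. In its paragraph on AUC, the same section says: "Samples that are BLQ at all other time points will be treated as missing data in WinNonlin".

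Other rules in the PK SAP state what happens in both outputs:
- Elimination-related parameters with more than 20% extrapolation "will be presented in the listings but excluded from the calculation of summary statistics" (3.6).
- On dosing deviations, 3.3.3 says: "Subjects with dosing deviations will be reported in the listings but excluded from the summary tables".
- Extrapolated AUC0-24 and AUC0-8 are listed and summarised, each with a footnote (3.6).

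Section 3.3.3 says in general that calculated parameters are both listed and summarised, and it tabulates a metabolite-to-parent ratio for Cmax. Neither statement has an exception for a withheld Cmax. Section 6.3 plans only a concentration listing. Individual and summary parameter values share Tables 1.1.2 to 1.1.4 in Section 6.1.

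**The concern.** Two different profiles trigger the rule. In one, the next scheduled sample was drawn, assayed and BLQ, so the concentration is known to have fallen. In the other, nothing was measured after the peak, and the concentration may still have been rising. Withholding Cmax is reasonable in the second case. In the first it discards an observed maximum because of a result that itself shows the fall.

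The first case can be foreseen. PK SAP 3.3.1 refers to the short plasma half-life of drug and metabolite, and 3.6 already provides for t_last before 24 h and before 8 h.

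Maximum plasma concentration is a named secondary PK parameter (Protocol 3.2). The profiles caught by a BLQ result tend to be those with low concentrations. If their Cmax also leaves the summaries, the exclusion is selective and summary Cmax is pushed upward. If the value is missing only from the individual display, the summary is unbiased but rests on a Cmax that is not shown for that subject. Two programmers could both follow the text and produce different Cmax tables.

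**Working it through.** The plan gives no figure to reproduce. There is no LLOQ, no expected concentration and no sample-size calculation.

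**1. Rule trace.** Samples are planned at 1, 2, 4, 8 and 24 h after each dose (PK SAP 2.2, Table 1).
- Peak at 8 h, 24 h sample BLQ: t_last = 8, t_max = 8, Cmax withheld.
- Peak at 8 h, 24 h sample missing: t_last = 8, t_max = 8, Cmax withheld, same footnote.

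The T_last definition alone produces this. The BLQ-as-missing sentence is not needed.

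**2. When a BLQ result triggers the rule.** Assume a mono-exponential fall from t_max. The next sample is BLQ if Cmax × 2^(−gap/half-life) < LLOQ, that is, if Cmax/LLOQ < 2^(gap/half-life). The half-lives are assumptions.

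| Peak → next sample | Gap | Half-life | Cmax/LLOQ below |
|---|---|---|---|
| 4 h → 8 h | 4 h | 2 h | 2^2 = 4 |
| 4 h → 8 h | 4 h | 4 h | 2^1 = 2 |
| 8 h → 24 h | 16 h | 2 h | 2^8 = 256 |
| 8 h → 24 h | 16 h | 4 h | 2^4 = 16 |
| 8 h → 24 h | 16 h | 6 h | 2^(16/6) = 6.3 |

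An early peak triggers the rule only near the LLOQ. Across the 16-hour gap the rule can trigger well above it.

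**3. Subjects lost if the value leaves the summaries.** Five subjects per cohort randomised 4:1 give 4 active (PK SAP 2.1). Pooling Parts One and Two by dose gives 8 (3.3.1). One exclusion removes 1/4 = 25% or 1/8 = 12.5%. If the lowest of n lognormal values is dropped, the geometric mean rises by about 7%, 14% and 21% for n = 4 at between-subject CVs of 20%, 40% and 60%, and by about 4%, 8% and 12% for n = 8 (400,000 draws; the CVs are assumptions).

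**4. Average effect, allowing for how often the rule triggers.** This is an illustrative one-compartment subcutaneous model with 200,000 subjects per scenario. Samples at 1, 2, 4, 8, 24 and 168 h were drawn within their windows, with 15% residual error, exposure CV of 30% or 50%, and rate-constant CV of 0, 25% or 50%. The result compares geometric mean Cmax among all subjects with a quantifiable sample with that among those left after the rule.

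Early-peaking kinetics (ka/ke per hour 0.35/0.30, 0.6/0.2, 0.7/0.5, 1.0/0.3):

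| LLOQ as % of median Cmax | Profiles affected, p | At least 1 of 4 affected, 1−(1−p)^4 | Rise in geometric mean |
|---|---|---|---|
| 5% | 0–0.8% | 0–3% | 0–0.5% |
| 10% | 0.01–2.3% | 0.05–9% | 0–1.3% |
| 25% | 1.0–9.6% | 4–33% | 0.4–6.1% |
| 50% | 16.6–28.0% | 52–73% | 6.3–15.1% |

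Slower kinetics (ka/ke 0.2/0.2 and 0.35/0.15) have typical peaks at 1/0.2 = 5.0 h and ln(0.35/0.15)/(0.35−0.15) = 4.2 h. With the LLOQ at 10%, 3.4–13.5% of profiles are affected, the rise is 1.4–6.2%, and at least 98% of the affected profiles have their observed peak at 8 h or later.

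If the value leaves only the individual display, the rise is 0%.

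**5. Is the withheld number a usable Cmax?** In the early-peaking runs the median withheld value is roughly 90–105% of the true peak for observed peaks at 1 to 4 h, and 83–100% for peaks at 8 h. This supports reporting it in both cases, with a lower-bound flag in the second.

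**The case against.** Four points can be made for the plan.

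- **The footnote is sometimes right.** A reader might infer that it is inaccurate for every profile with a collected BLQ sample. The sampling schedule does not support that. After an 8 h peak nothing is drawn for 16 hours, so the true maximum may lie between samples and a sampling-time caveat is fair. The charge of inaccuracy holds clearly only for peaks at 1 to 4 h.
- **The scope can be guessed.** Individual and summary values share the same tables, and 3.6 asks for an explanation beside values excluded from summaries, which the Cmax footnote resembles. A Cmax that is not reportable would ordinarily leave the summary and the ratio too. That is the more natural reading, but it is not stated, and it is also the reading that creates the bias.
- **Nothing is lost.** The number still appears as C_last and in the concentration listing. This stands, but it does not put the value into the Cmax summary or the ratio.
- **The effect may be nil.** Without an LLOQ, nobody can say from the documents whether the rule will ever trigger. A reader might infer from the larger simulated rises that reported Cmax will be materially inflated. With early-peaking kinetics, rises above about 1.3% need an LLOQ at 25–50% of median Cmax, and nothing in the documents supports such a limit.

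The rule's other consequences are already covered. The terminal slope needs "at least 3 data points not included" Cmax, and if it "is not estimable, the partial area will not be calculated" beyond the last observed point. Only Cmax, T_max and the Cmax ratio need new wording.

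**Conclusion.** The point stands as a defect in one reporting rule, of low to moderate importance. PK is a secondary, descriptive endpoint, and the primary safety objective is untouched.

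Three conclusions rest on the text alone. The rule does not separate BLQ from missing. For peaks at 1 to 4 h with the next scheduled sample BLQ, it suppresses a valid Cmax under the wrong explanation. It also leaves the summary and the Cmax ratio unaddressed.

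The upward bias is conditional on the value leaving the summaries. Its size rests on an assumed LLOQ and assumed kinetics: at most about 1.3% for an LLOQ at 5–10% of median Cmax with early peaks, 1.4–6.2% at 10% with slower kinetics, and up to 15.1% with early peaks only if the LLOQ is as high as 50%. It is negligible if levels peak early and lie well above the LLOQ. The documents do not support a claim that the rule is wrong where later samples are missing. There it is reasonable and should stay.

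**What to change.** Replace the t_last = t_max rule in PK SAP 3.6 with two cases.

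1. **Next scheduled sample after t_max collected, evaluable and BLQ:** list and summarise Cmax and T_max. Keep the Cmax metabolite-to-parent ratio where both analytes have a Cmax. Flag that no quantifiable value followed the peak. If that next sample lies across the 8-to-24 h gap or a longer one, also flag Cmax as a possible lower bound.
2. **Next scheduled sample missing or not evaluable:** keep the suppression and the existing footnote, even if a much later sample such as Week 1 is BLQ. State that the value is also excluded from the summaries and from the Cmax ratio.

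No new text is needed for the terminal-phase parameters or partial areas, which 3.5 already handles.

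The cost is one rule and its footnotes, with no new samples or data. Reported Cmax may be slightly lower if some profiles lie near the LLOQ.
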